Consistent with the desire of clinic staff to integrate this project into their standard workflows, we will use automated codes to manage interventions so that eligible patients get initial HPV vaccines on time and P/C are prompted to repeat vaccination, as recommended. Our EHR tools rely on Reporting Workbench, a population management tool in Epic which will be customized to include tools needed for tracking completion of HPV vaccination at the 4 intervention clinics. The registry will list patients' HPV vaccination history as well as key demographic variables for the intervention (e.g., name, address, preferred language). We will select a cohort of approximately 1,038 P/C of patients from the 4 clinics, randomized to intervention arms (UC, Auto, and Auto-Plus) stratified by clinic, sex, and language preference (English, Spanish, other) to ensure a nearly balanced distribution of clinic, sex, and language preference among study arms. The registry will generate 2 real-time reports: 1] HPV vaccination outcomes (i.e., date of vaccination events, and whether the event represents series initiation, second dose, and/or series completion); and 2] PREVENT intervention activities (i.e., date of

Table 3: Schedules of Measures (part.=participants; T=time, Y=year; M=month)								
Variable	Data source	How measured	Proctor/ RE- AIM domain	Т				
Aim 1: Bootcamp Translation (BCT)								
Rural parent-/ caregiver- & provider-driven adaptations/ program acceptance	Parents / providers	Notes from BCT sessions	Adaptations, Acceptance	Y 1				
Aim 2: PREVENT Randomized 0	Controlled Trial (I							
Reach of RCT – primary outcome (next needed HPV vaccine dose)	EHR; vendor logs	N part. receive program/ N anticipated, reasons	Reach	6 m				
Reach of RCT – secondary outcome (completion of HPV vaccine series)	EHR; vendor logs	N part. receive program/ N anticipated, reasons	Reach	6 m				
Effectiveness of RCT – primary outcome	EHR	N C/A complete next HPV vaccine dose/ N anticipated	Effectiveness	6 m				
Effectiveness of RCT – secondary outcome	EHR	N C/A complete all doses of HPV vaccine  / N anticipated	Effectiveness	13 m				
Aim 3: Tertiary and Qualitative	Outcomes							
Moderators (e.g., sex of parent, sex of child, age, ethnicity, etc.)	EHR data	Effectiveness of intervention by presence of moderator	Equity	6 m				
Parent/caregiver reactions	Interviews	Coded transcripts	Acceptance	Y 3				

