- Interactive web-based coaching tool: Live calls will be facilitated by an interactive web-based coaching tool that prompts patient navigators during live phone calls with P/C on how to best respond to varying types and levels of P/C vaccine hesitancy. This tool will be developed by Drs. [name] and [name] in partnership with HCl's bioinformatics core. P/C identified vaccine hesitancy barriers may fall within the broad domains related to vaccine confidence, vaccine complacency, and vaccine convenience (Figure 2).
- Patient navigators: trained staff who promote healthful behaviors by addressing barriers to care. Navigators can respond to the cultural needs of their patients—such as values of *personalismo* or *respeto*. 127, 128

**C.5.c.** Intervention Process: Focused on HPV vaccine series completion. The BCT process will define the format (mode and frequency) and content of messages to promote vaccine series completion. The clinic-level analysts will generate real-time lists of patients who have initiated the HPV vaccine and are due for a follow-up dose, stratified by age group (11–14 vs. 15–17). The list will include adolescents age 11–14 years who have completed an initial dose of the HPV vaccine and are due for a second dose (within 6-12 months) and those aged 15–17 who are due for a second or third dose. While Auto and Auto-Plus interventions for series

completion may use some of the same components as vaccine initiation (automated calls, live calls, text messages, emails, and mailings), some notable differences will likely exist. HPV vaccine initiation may bundle recommendations for HPV and for other needed vaccines (e.g., "[Patient name] is due for the following vaccines: HPV; meningococcal; Tetanus, Diphtheria, Pertussis"), whereas series completion will not need bundled messages. Series completion reminders will include scheduling and appointment reminders.

**C.5.d. Evaluation:** Based on our previous research and conversation with clinic staff, we have designed Phase I to include multiple components. Using the Proctor Implementation and RE-AIM frameworks, we will track intervention reach and effectiveness. We will conduct one-on-one interviews with participants and debrief interviews with HCP to illuminate persistent barriers to HPV vaccination uptake and factors important to program acceptability, maintenance, and sustainability. **Table 3** summarizes these measures.

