Program Effectiveness: We will assess intervention effectiveness for each of the three study arms, calculated as the proportion of eligible children/adolescents who received any HPV vaccine within 6 months and 13 months (series completion by one year) of randomization. We will assess the proportion of C/A who initiated HPV vaccination, those who received the next needed dose and the percent who completed the series.

Study Design: We propose a 3-arm RCT to compare rates of completing the next step in the HPV vaccination series at 6 months and completing the HPV vaccination series at 13 months between Auto, Auto-Plus, and UC arms. P/C of C/A who have not completed the HPV vaccination series will be randomized 1:1:1 to study arms, with separate randomizations within each clinic (Ocean Shores, Aberdeen, Elma, or Yelm) and patient-level HPV vaccination initiation status (series initiated or not initiated). Participants will be assessed for eligibility and, if eligible, enrolled within the 4 clinics at their first visit time during the 12-month study period, with a total participant time on study of 13 months, for a total of 25 months of enrollment, execution, and follow-up.

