Statistical Approaches: The primary comparisons are between the rates of completing the next step in the HPV vaccination series at 6 months in the Auto, Auto-Plus, and UC arms (Primary Outcome), and between the rates of completing the HPV vaccination series at 13 months (Secondary Outcome). Completing the next step in the vaccine series and completing the vaccine series outcomes will be compared via logistic generalized estimating equations (GEE) models, 129, 130 with bias-reduced robust sandwich variance estimators 131 clustered by clinic. These logistic GEEs will be adjusted for P/C and patient features that may influence HPV vaccination series next step and completion, including age, sex, race/ethnicity, rurality, and HPV vaccination initiation status at study enrollment. Models comparing the Auto, Auto-Plus, and UC groups, will also include study arm. Comparisons between the study arms of the next-step and series-completion endpoints will be performed separately. For each endpoint, pairwise differences between arms will be assessed with a Bonferroni correction to achieve type I error control at 0.05, with p<0.017=0.05/3 needed for statistical significance. Predefined subgroup analyses will be performed by P/C and/or patient sex, age group, race/ethnicity, rurality, and HPV vaccination initiation status at study enrollment, and each of these characteristics will be assessed for effect moderation. Since next step completion and series completion will be captured via the EHR and the state-wide vaccine registry, we anticipate little missing data for these outcomes. Statistical Analysis and Power: Based on the **Table 2**, there are 1038 patients in the appropriate age range, of whom <50% will have completed the HPV vaccination series, for at least 519 patients within the eligible age range who have not yet completed the HPV vaccination series, with at least 173 in each study arm. 173 participants per study arm will ensure >80% power for detecting rate differences for both the next step endpoint and series completion endpoint exceeding 0.17, under the Bonferroni statistical significance benchmark of p<0.017. If the completion endpoint rate is 50% in the Auto-Plus arm and is 33% in the UC arm (rate difference 0.17), then the proposed study will have 80% power for detecting a difference by arm. Moderators: We will assess differences across study arms in our secondary outcome: missed opportunities, defined as patients who receive other recommended vaccinations, but not HPV. We will also explore possible moderators of effectiveness: age (11– 14, 15–17), ethnicity (Hispanic vs. non-Hispanic white), sex (male vs. female vs. other), language (Spanish vs. English), poverty status (<100% Federal Poverty Level vs ≥100% Federal Poverty Level), and insurance status (commercial vs. Medicaid vs. other). Thus, we will consider **sex a biological variable**, an important distinction because of differing rates of HPV vaccination and barriers faced by adolescent males and females. 132-135 By assessing differences in effectiveness across the life course of ages 11-14 and 15-17, we will understand differences in groups for whom 2 doses and 3 doses of the vaccine is recommended. Each potential moderator will be tested separately by considering its main effect and interaction with study arm in the logistic mixed effects models (Aim 2). Evidence of differential intervention effectiveness will be supported by an overall test of

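### The adjusted models use vaccine history only as initiated or not, leaving out time since the last dose and, among initiated 15–17-year-olds, whether one or two doses remain: a modest loss of precision, not bias

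*Combined protocol and SAP*

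**What the plan says.** Section C.5.d (Statistical Approaches) compares the arms on the next needed dose at 6 months and on series completion at 13 months. It uses logistic GEE models clustered by clinic, with covariates "including age, sex, race/ethnicity, rurality, and HPV vaccination initiation status at study enrollment". C.5.d (Study Design) randomizes separately within clinic and "patient-level HPV vaccination initiation status (series initiated or not initiated"), so the vaccine-history covariate is binary. No other vaccine-history covariate, subgroup or moderator is named. Age is a covariate, and age 11–14 versus 15–17 is a moderator that the plan links to "groups for whom 2 doses and 3 doses of the vaccine is recommended".

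Section C.5.c shows what the initiated group contains. Children aged 11–14 who have had dose 1 "are due for a second dose (within 6-12 months"). The list also holds "those aged 15–17 who are due for a second or third dose", and no interval is given for that age group. The registry in C.5.b will hold the "date of vaccination events, and whether the event represents series initiation, second dose, and/or series completion".

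On who is randomized, C.5.d covers parents and caregivers of children "who have not completed the HPV vaccination series will be randomized 1:1:1 to study arms". The lists in C.5.b and C.5.c are instead of patients due for a dose.

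**The concern.** Both outcomes depend on where a child stands in the series at randomization. A 15–17-year-old awaiting dose 3 completes with one visit, while one awaiting dose 2 needs two. Both are coded as initiated and both fall in the same age band, so neither age nor an age-by-initiation term can separate them. Likewise, a child of 11–14 who had dose 1 shortly before randomization may have little of the 6-month primary window in which dose 2 is due. One whose dose was long ago can be vaccinated at once. No named covariate tells them apart.

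Two things are at stake. Outcome variation that baseline data could explain stays in the residual, in a trial with little spare power. And for children with one dose left, 13-month completion is the same event as the next needed dose, read later. The planned subgroups by initiation status and by age cannot show how much of the secondary endpoint adds to the primary.

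**Working it through.** **1. The plan's own power.** Inputs (C.5.d): 173 per arm, 50% versus 33%, alpha 0.05/3. Two-sided testing is assumed, because the plan does not say.
- SE = √[(0.50×0.50 + 0.33×0.67)/173] = 0.0522, and 0.17/0.0522 = 3.258. The critical value is 2.394.
- Power = Φ(3.258 − 2.394) = 80.6%. With pooled variance under the null it is 79.6%, and 174–175 per arm are needed, depending on whether 0.017 or 0.05/3 is used. The stated 80% reproduces, with almost no margin.

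**2. Who is affected.** Inputs: Table 2 counts (158, 241, 73, 566; total 1038) and rates. Assumption: ages spread evenly, so 2/7 are 11–12, 5/7 are 13–17, and 2/5 of the latter are 13–14. Not initiated = count × (1 − initiation rate). Initiated but incomplete = count × (initiation rate − completion rate). For Yelm at ages 11–12: 566 × 2/7 × (1 − 0.483) = 83.6 not initiated. Summed over clinics:

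| Group | Children | Share | Doses still needed |
|---|---|---|---|
| 11–14, not initiated | 282.6 | 42% | 2 |
| 15–17, not initiated | 184.6 | 27% | 3 |
| 11–14, initiated | 142.5 | 21% | 1 |
| 15–17, initiated | 68.0 | 10% | 1 or 2 |
| Total | 677.7 | 100% | |

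Initiated share = (142.5 + 68.0)/677.7 = 31%. It runs from 27% (nobody aged 11–12) to 38% (everybody aged 11–12). Age band and initiation together fix doses still needed for (282.6 + 184.6 + 142.5)/677.7 = 90%.

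**3. Completion at 13 months, doses still needed.** Assumed usual-care rates are 75/25/5% with one/two/three doses left, and initiated 15–17-year-olds are split evenly between one and two.
- Residual variance given age band × initiation: 0.417×0.1875 + 0.272×0.0475 + 0.210×0.1875 + 0.100×0.25 = 0.1556.
- Variance that doses still needed explains inside the 15–17 initiated group: 0.100 × 0.0625 = 0.0063.
- Cut: 0.0063/0.1556 = 4.0%. Simulation of 6,000 two-arm trials at these rates moved power from 91.8% to 92.6%. Flatter rates give almost nothing.

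**4. Next dose at 6 months, timing.** Assumptions: not-initiated rate 33%, initiated share 31.1%, and timing classes of equal size. Cut = 0.311 × between-class variance ÷ residual variance given initiation.
- Not yet due/in window/overdue at 10/60/25%: 0.311 × 0.0439/0.2196 = 6.2%. Simulation of the same rates gave a 5.5% cut, with power moving from 80.1% to 82.6%.
- No not-yet-due children, 60/25%: 0.311 × 0.0306/0.2283 = 4.2%.
- No not-yet-due children, 50/30%: 0.311 × 0.0100/0.2270 = 1.4%.
- Rates of 30/40/30%: no material change.

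**5. Range of the gain.** Over mild to strong contrasts, with 30% or 40% initiated, power = Φ(3.258/√(1 − R²) − 2.394). The sample-size equivalent is 1 − (1 − R² full)/(1 − R² age + initiation).
- Smallest (next dose, mild, 30% initiated): R² 0.015 to 0.019, power 81.3% to 81.5%, sample size 0.4%.
- Largest (next dose, strong, 40% initiated): R² 0.116 to 0.197, power 85.8% to 89.3%, sample size 1 − 0.803/0.884 = 9.2%.
- Completion, strong, 40% initiated: R² 0.261 to 0.308, power 91.9% to 93.6%, sample size 6.3%.

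Logistic simulation (3,000 replicates, 30% initiated, independent children) gave extra gains of 0.1 to 3.1 points. Type I error was 0.013 to 0.021 for both adjusted models, against a nominal 0.0167 (Monte Carlo SE 0.002).

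**The case against.** The strongest reply is that age already does much of this work. It is in both models, the plan links the age bands to series length, and with initiation it settles doses still needed for about 90% of non-completers. That stands, and it is why the gain in step 5 is counted beyond age and initiation. It does not reach time since last dose, or the initiated 15–17-year-olds.

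Second, the covariate list is introduced as a list of inclusions, so finer coding is not excluded. True, but an open list prespecifies nothing, and a covariate added after the data are seen is open to challenge.

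Third, the not-yet-due group may not exist. The reminder lists are of patients who are due, and section C.7 aims to avoid outreach to those who are not. The documents leave this open. Without that group, the examples in step 4 still give a variance cut of about 1 to 4%.

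Fourth, the rates by dose stage are assumptions, and the simulations used individual-level logistic tests. The plan uses GEE with a bias-reduced sandwich variance over four clinics, and the gain has not been shown under that analysis. This stands and limits how firmly the size can be put.

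A reader might infer that pooling unlike children biases the arm comparison or inflates type I error. The documents do not support this: assignment is randomized within initiation status, and simulated type I error stayed near nominal.

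**Conclusion.** The point holds as a modest and avoidable loss of precision. The models carry no information on time since last dose, or on one versus two doses left among initiated 15–17-year-olds. About 31% of non-completers are initiated, on an even age spread. The likely gain from finer adjustment is about 0 to 3 power points, or 0 to 9% of the sample size, under assumed stage-specific rates, two-sided alpha of 0.05/3 and individual-level tests.

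It would go too far to say that the models ignore how many doses are needed, since age and initiation carry most of that. Nor does this point call for a different sample size. That completion and next dose coincide for one-dose-left children is a property of the endpoints. It is a reason to report completion by doses left, not an analysis error.

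**What to change.** In C.5.d (Statistical Approaches), keep initiation status in both models, because C.5.d makes it a randomization stratum. Replacing it with doses still needed would lose that stratum in a main-effects model: two doses left means not initiated at 11–14 but initiated at 15–17. Add two baseline covariates from the dated EHR/registry record:

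- **Doses still needed at randomization**, with age band and its interaction with initiation in the model. It then adds information only among initiated 15–17-year-olds, so one indicator (one versus two left) is enough.
- **Time since last dose at randomization** for initiated children, set to zero for the others with the initiation indicator retained. Use elapsed time rather than a due/overdue class, because C.5.c gives an interval only for ages 11–14 awaiting dose 2. Fix its functional form in advance: a straight line would recover less than step 4 shows if uptake rises and then falls with time.

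Report 13-month completion by arm, descriptively, by doses still needed. Reconcile C.5.b, C.5.c and C.5.d on whether children not yet due are randomized.

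The cost is SAP wording, two derived variables and about three model parameters (the interaction, the indicator and a linear time term; a curved form adds one or two). No new data or participants are needed. The drawback is sparse levels: 31% of 519 is about 161 initiated children, or 54 per arm, so state in advance the rule for merging or dropping a level.

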# C.5. Aim 2: Test a set of automated reminders (defined during Aim 1) on timely receipt of next needed HPV vaccine dose and on series completion.

We hypothesize that Auto and Auto-Plus interventions will be more effective than usual care, and Auto-Plus will be more effective than Auto at increasing receipt of the next needed HPV vaccine dose and on series completion. We will implement and evaluate the intervention in 4 clinics using an individual-RCT design (IM Steps 5 and 6). Our quantitative evaluation will assess intervention effectiveness and reach. We will gather P/C-, patient- and HCP-level data to identify possible program enhancements, as well as barriers and facilitators to adoption, implementation, and maintenance.

**C.5.a.** Convene Teams and Train Staff: Each participating clinic will convene an implementation team comprised of a clinic champion, clinic coordinator, and relevant laboratory and administrative personnel whom we will select for their ability to facilitate the intervention within the clinic settings. Once the team is formed, members of the PREVENT research team and clinic staff will train the participating clinics in delivering the intervention. Staff training will take place during a half-day session (with additional phone support) and will address procedures for identifying P/C of eligible patients and tracking automated outreach (e.g., automated phone calls, text messages). Clinics will receive training specific to the Auto-Plus components, such as the live phone call and patient navigation protocols using as computer assisted interactive system.

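### Optional efficiency gain, not an error: a three-arm Shaffer step-down would keep every Bonferroni rejection and add power for the second and third comparisons at the same 0.05 familywise level

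*Combined protocol and SAP*

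**What the plan says.** The multiplicity rule is in section C.5.d, under Statistical Approaches. Within each endpoint, the plan states that "pairwise differences between arms will be assessed with a Bonferroni correction to achieve type I error control at 0.05". It then spells out the cut-off that every comparison must meet: "with p<0.017=0.05/3 needed for statistical significance". The two endpoints form separate families: "Comparisons between the study arms of the next-step and series-completion endpoints will be performed separately". No step-down, closed or gatekeeping procedure appears anywhere in the document.

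The introduction to Aim 2 (section C.5) hypothesises all three contrasts: "Auto and Auto-Plus interventions will be more effective than usual care, and Auto-Plus will be more effective than Auto".

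Under Statistical Analysis and Power, 173 participants per arm are said to give more than 80% power for "rate differences for both the next step endpoint and series completion endpoint exceeding 0.17" at the Bonferroni threshold. The worked case is 50% in Auto-Plus against 33% in usual care (UC) on series completion. No rate is given for the Auto arm. The planned analysis is a covariate-adjusted logistic GEE with "bias-reduced robust sandwich variance estimators 131 clustered by clinic".

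**The concern.** Nothing in the rule is invalid; the point is efficiency. Single-step Bonferroni treats the three pairwise nulls as if any combination of them could be true. With three arms that is not so. If Auto differs from UC, Auto-Plus cannot equal both, so at most one of the remaining nulls can hold. Bonferroni keeps paying for a configuration that the first rejection has already ruled out.

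This matters because Aim 2 makes all three contrasts hypotheses, so a second or third rejection is part of what the trial sets out to show. The sample size is limited by the patient pool of four small clinics, so power that needs no extra patients deserves consideration.

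**Working it through.** **Inputs from the plan.** Familywise level 0.05 per endpoint; threshold 0.05/3 = 0.01667; 173 per arm; 1:1:1 allocation; UC 33%, Auto-Plus 50%.

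**Assumptions.** Two-sided tests (sidedness is not stated, but two-sided reproduces the stated power); independent binomials; pooled z tests; the Auto rate, which the plan does not give.

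**Step 1: the plan's own figure.** Power = Φ[(d − z·√(2p̄q̄/n)) / √((p₁q₁ + p₂q₂)/n)].
- d = 0.17, p̄ = 0.415, and z for 0.05/3 two-sided = 2.394.
- √(2 × 0.415 × 0.585/173) = 0.05298.
- √((0.33 × 0.67 + 0.50 × 0.50)/173) = 0.05218.
- (0.17 − 2.394 × 0.05298)/0.05218 = 0.827, and Φ(0.827) = 79.6%.

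The stated 80% reproduces.

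**Step 2: why the step-down is valid.** There are three cases.
- All three nulls true: a false claim requires the smallest p-value to fall below 0.05/3, which has probability at most 3 × 0.05/3 = 0.05.
- Exactly one null true: that pair is never tested above 0.05, so the risk is at most 0.05.
- Exactly two nulls true: impossible, because two equalities among three arms imply the third.

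Familywise error is therefore at most 0.05 given valid p-values. Any p-value below 0.05/3 is still rejected, so no Bonferroni rejection is lost.

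**Step 3: size of the gain.** 1,000,000 simulated trials per scenario. Cells show Bonferroni → step-down, in per cent.

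| UC/Auto/Auto-Plus | Auto vs UC | Auto-Plus vs UC | Auto-Plus vs Auto | At least two | All three |
|---|---|---|---|---|---|
| 33/38/50 | 7.8→15.9 | 79.9→82.3 | 43.8→57.7 | 46.9→67.5 | 0.85→4.7 |
| 33/40/50 | 14.9→26.5 | 79.9→81.4 | 29.3→43.4 | 40.9→63.4 | 1.0→5.7 |
| 33/41.5/50 | 22.6→36.2 | 79.9→81.2 | 20.2→33.0 | 39.8→62.7 | 1.05→5.9 |
| 33/45/50 | 46.4→60.5 | 79.9→82.4 | 6.8→14.3 | 48.6→68.9 | 0.8→4.5 |

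- The chance of any rejection is identical under both rules (82–84% in these rows).
- Auto equal to UC or to Auto-Plus (one Aim 2 hypothesis is then false): each true difference goes from 80% to 86%.
- Rates of 33/50/67%, which go beyond the plan's worked case: adjacent pairs 80% to 90%, all three 61% to 80%.
- Bonferroni rejections lost: none in any scenario.

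**Step 4: what it costs.**
- Familywise error with all arms equal is the same under both rules: 4.45% at 33% and 4.1% at 50%.
- With exactly one true null pair, the false-claim rate rises from about 1.6% to 4.6% (33/50/50) or 4.9% (33/33/50). In the limiting case 33/33/90, a run of 400,000 trials gives 5.0%.
- At least one step-down claim has p at or above 0.05/3, and so disagrees with its 98.33% interval, in 23–26% of trials in the tabulated scenarios, 15% when Auto equals another arm, and 19% at 33/50/67.

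**The case against.** - **The plan is already sound.** It fixes one standard rule in advance, with a threshold and power that agree. Preferring another rule is a judgement about value, not a correction. This stands, and it is why the point is offered as an improvement.
- **Shaffer is not the only choice.** A global 2-df chi-square test at 0.05 followed by pairwise tests at 0.05 is also a closed procedure. In simulation it does slightly better at 33/33/50 (each true difference 87.6%, against 86.3% for Shaffer), with familywise error of 5.03% when all arms are at 33%. This is fair. Shaffer's advantages are that it needs only the three planned p-values and can never lose a Bonferroni rejection.
- **The gain is small where the plan claims power.** Auto-Plus vs UC gains only 1.4–2.5 points when Auto lies between them. The larger gains concern differences below 0.17, on an Auto rate the plan never states. This also stands.
- **The strongest objection is that the argument needs valid p-values, and the planned robust variance rests on four clinics.** An illustrative simulation used an arm-only model with bias-reduced variance, clinic sizes in proportion to Table 2 and no clinic effect, at 33/33/50. With a normal reference, the false-claim rate for the null pair is about 12% under Bonferroni and 17% under the step-down. With all arms at 33%, familywise error is about 29% under both. With a t reference on 3 degrees of freedom, the 33/33/50 false-claim rates are about 2.5% and 5%. The plan names no reference distribution. The variance question is therefore separate and larger, and it undermines both rules. It should be settled before or together with any relaxation of the threshold, because the step-down adds false claims when p-values are too small.

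**Conclusion.** The point holds as an inexpensive improvement to a valid plan. Given valid p-values, the step-down controls familywise error at 0.05 per endpoint, as the plan intends, and can only add rejections. At the plan's worked rates with Auto assumed between 38% and 45%, it adds about 8–14 points for Auto vs UC and 7–14 for Auto-Plus vs Auto, and the mean number of rejections rises from 1.23–1.33 to 1.50–1.57.

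It does not rescue Aim 2 as a whole. Full support for all three hypotheses remains improbable at these rates, and that is a sample-size limit.

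The validity of the rule follows from logic. The size of the gain is illustrative: it rests on independent binomials, 173 per arm and an assumed Auto rate. Neither these figures nor the plan's 80% describes the adjusted GEE clustered on four clinics. Error control is within each endpoint and does not cover the two endpoints jointly.

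**What to change.** Before any outcome data are seen, replace the single-step rule with the following, applied separately to each endpoint. Test the smallest of the three pairwise p-values at 0.05/3. If it is significant, test each of the other two at 0.05; otherwise stop.

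Report 98.33% intervals for all three differences, and state that the step-down decides significance and may disagree with an interval. Keep 173 per arm and 80% as the planning figure for the first step, labelled as resting on independent binomials. Settle separately how valid p-values will be obtained with four clinics.

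The change takes one or two SAP sentences and alters neither sample size nor data collection. Its drawbacks are the test-interval mismatch and the higher false-claim rate when exactly one pair is truly null, which stays within 0.05. If the team prefers tests and intervals that always agree, it can keep Bonferroni and give that reason in the SAP.

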
the potential moderator by study arm interaction effects.

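### The moderator analysis cites an Aim 2 mixed model that the plan never defines; run in the defined Aim 2 GEE with clinic-clustered variance, its overall interaction test is not usable with four clinics

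*Combined protocol and SAP*

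**What the plan says.** The relevant text is in C.5.d.

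- **Outcome model.** Under Statistical Approaches, both Aim 2 endpoints "will be compared via logistic generalized estimating equations (GEE) models", with "bias-reduced robust sandwich variance estimators 131 clustered by clinic". The listed adjustment covariates are age, sex, race/ethnicity, rurality and initiation status; clinic is not among them. No working correlation, reference distribution or small-sample degrees of freedom are given. The same paragraph announces subgroup analyses and says that those characteristics will also be examined as effect modifiers, without naming a model.
- **Moderator model.** Under Moderators, each moderator is tested separately by its main effect and "interaction with study arm in the logistic mixed effects models (Aim 2". Support for moderation comes from an overall test of "the potential moderator by study arm interaction effects". No random effects, estimation method or test statistic is given for a mixed model anywhere in the document.
- **Moderators.** Four have two levels (age group, ethnicity, language, poverty), for example "ethnicity (Hispanic vs. non-Hispanic white". Two have three levels: "sex (male vs. female vs. other" and "insurance status (commercial vs. Medicaid vs. other".
- **Design.** The opening of C.5 states: "We will implement and evaluate the intervention in 4 clinics using an individual-RCT design". C.5.b and C.5.d describe the randomisation strata differently, but both include clinic.

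**The concern.** The moderator text refers back to a model that is not there. An analyst must either invent a mixed model or fall back on the one Aim 2 model that exists, the clinic-clustered GEE. The subgroup sentence, which directly follows the GEE description and names nothing else, makes the second route a natural reading.

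That route is a problem because the clinic-clustered variance is built from four clinic contributions, while the overall test asks it to support 2 or 4 degrees of freedom at once. At stake are the conclusions about who benefits: Table 3 assigns moderators to the equity domain, and the Innovation section presents attention to rural subgroups, Hispanic persons in particular, as a main contribution of the trial.

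**Working it through.** **1. The plan's own figure.** The plan gives no figure for the moderator test. Its one computed design figure is 80% power for 50% versus 33% with 173 per arm at 0.05/3. With unpooled variance and a two-sided test: 0.17 / √[(0.33×0.67 + 0.50×0.50)/173] = 0.17/0.0522 = 3.26; 3.26 − 2.39 = 0.86; Φ(0.86) = 80.6%. Pooled variance gives 79.6%. The figure reproduces when participants are treated as independent, so the sample size is not in question here.

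**2. Degrees of freedom.** With 3 arms and a k-level moderator, the interaction has (3 − 1)(k − 1) terms: 2 for k = 2 and 4 for k = 3.

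**3. Rank.** The centre of the sandwich is ΣU_gU_g′ over the four clinics. The estimating equations force ΣU_g = 0, so its rank is at most 4 − 1 = 3. Without bias reduction, the 4×4 interaction block is singular and a 4-df Wald test cannot be computed. This is algebra and needs no simulation. Bias reduction makes the block invertible but adds no clusters.

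**4. Size under no moderation.**
- From the documents: 519 children, 1:1:1 allocation, and clinic sizes in proportion to Table 2 (158, 241, 73 and 566 of 1,038, which halve to about 79, 120, 37 and 283).
- Assumed: outcome near 35%; moderator split 30/70 or 30/55/15; working independence; clinic intercept SD of 0 or 0.3.
- Results are ranges over separate sets of runs, nominal 5%:

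| Test | 2 df | 4 df |
|---|---|---|
| Clinic-clustered bias-reduced (CR2) Wald, chi-square | 37–44% | about 98% |
| Same, F with 3 denominator df | about 20% | about 93% |
| GEE with model-based variance | 4.4–5.7% | 4.0% |
| Logistic, clinic fixed, likelihood ratio | about 5–7% | about 5–7% |
| Logistic, random clinic intercept, likelihood ratio | 5.0–5.5% | 6.4–7.4% |

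The random-intercept row used 1,000 runs per setting and clinic SDs of 0, 0.3 and 0.8. At a true 5%, the Monte Carlo standard error is √(0.05×0.95/1000) = 0.7 points for 1,000 runs and 1.3 points for 300, the smallest number used for 4 df.

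**5. Small-sample correction.** For the approximate Hotelling T² test, the denominator df are η − q + 1, and η was about 1.92.
- q = 2: 1.92 − 2 + 1 = 0.92. The test exists and rejects 0.1–0.2% under the null.
- q = 4: 1.92 − 4 + 1 = −1.08. No test exists.

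**6. Power of the corrected 2-df test.** The same interaction was placed on both active arms, with clinic SD 0.3 and 1,000 runs:

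| Interaction odds ratio | Hotelling-type correction | Clinic fixed, likelihood ratio |
|---|---|---|
| 2.7 | 1.3% | 55% |
| 4.5 | 1.9% | 88% |

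**The case against.** The best reply is that the moderator text names a mixed model, not the GEE, so the high rejection rates belong to a model it does not cite. That stands as a condition: the rates apply only if the conflict is resolved towards the Aim 2 GEE and its clinic-clustered variance. It does not remove the conflict, and the subgroup sentence leaves the GEE route open.

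Several stronger readings are tempting, and the documents do not support them:

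- **A mixed model must fail with four clinics.** A random-intercept model with a likelihood-ratio test rejected 5.0–7.4%. It is undefined in the plan, not shown to be invalid.
- **A mixed model is wrong because it is conditional while the GEE is marginal.** A logistic model with clinic as a fixed factor is also conditional on clinic, so this is no reason to prefer it.
- **No valid test exists in the GEE.** That is strict only for 4 df. For 2 df the small-sample correction keeps the error below 5%, at the price of almost all power. GEE point estimation is not at fault either; model-based variance behaved well.
- **Most moderators would appear significant by chance.** With a chi-square reference, the expected count is 4×0.37 + 2×0.98 = 3.4 to 4×0.44 + 2×0.98 = 3.7 of six, against 6×0.05 = 0.3. If the third sex category is empty (the documents give no count), it is 5×0.37 + 0.98 = 2.8 to 5×0.44 + 0.98 = 3.2, about half. The plan states no chi-square reference.

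It is also fair to say that the moderator work is exploratory, sits among the tertiary outcomes in Table 3, and drives no decision rule. That limits the weight of the point.

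**Conclusion.** The point holds in a limited form. The plan attributes the moderator test to an Aim 2 mixed model, while the only Aim 2 model it defines is a clinic-clustered GEE. That contradiction, and the rank limit of 3 for the uncorrected variance, follow from the text and from algebra.

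If the GEE route is taken, the overall interaction test rejects about 37–44% (2 df) and 98% (4 df) of the time with a chi-square reference when there is no moderation. An F reference reduces this only to about 20% and 93%. These rates depend on the assumed moderator prevalence, outcome rate and working independence, none of which the documents give. If a random-intercept mixed model with a likelihood-ratio test is used instead, no material failure was found. The change should be made before analysis, but the point concerns an exploratory analysis. It is not a finding about the primary comparisons.

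**What to change.** Replace the reference to Aim 2 mixed models with one stated model, and apply it to the effect-moderation analyses announced under Statistical Approaches as well:

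- A participant-level logistic regression with study arm, the moderator, arm-by-moderator terms, the planned covariates, and clinic as a fixed factor. Clinic is already a randomisation stratum. A moderator that is also a planned covariate enters once.
- An overall likelihood-ratio test of the arm-by-moderator terms, on 2 or 4 df, and not a Wald test from the clinic-clustered sandwich. State that its rejection rate is close to nominal (about 5–7% in simulation).
- If rurality is coded at clinic level, omit its main effect. Table 2 shows one rural percentage per clinic (40.1 for three clinics, 29.0 for the fourth), and such a variable is aliased with the clinic indicators. Its interaction with arm can still be estimated, because arm varies within clinic.
- A rule, set in advance, for collapsing sparse levels such as the third sex category.

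The cost is a few sentences in the analysis plan and three clinic indicator terms. No data collection, sample size or procedure changes.
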